10.1 EVALUABILITY

All subjects who provide informed consent and complete a screening visit are considered study participants. Study populations are defined as follows, with statistical analysis performed separately on each of the populations:

- Safety population, including all subjects who are randomized and have received at least one treatment of test article.
- Intent-to-treat (ITT) population (otherwise referred to the as the Full Analysis Set),
 including all subjects who are randomized, have a valid baseline ulcer measurement, and

complete at least one post-baseline visit. The ITT population is the primary efficacy population.

 Per protocol (PP) population, including those ITT subjects who complete the 6-week treatment period (or achieve a closed ulcer in < 6 weeks), receive only the initiallyrandomized treatment, have no significant protocol deviations, and meet the prerandomization inclusion/exclusion criteria. The PP population is the secondary efficacy population.

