8.2 METHODS USED TO MINIMIZE BIAS

Due to obvious differences in the physical appearance of the test articles, double-blinding of the study medication is not possible. However, assessments of the ulcer debridement status relating to the presence of non-viable necrotic tissue (primary objective) will be carried out in a blinded fashion by two independent assessors using digital photographs identified only by the subject number and date. Blinded assessment is intended to limit the occurrence of conscious and unconscious bias in the assessment and interpretation of the endpoints. In addition, randomization will be sequential according to a pre-determined, computer-generated randomization schedule. In this way the Investigator will not be able to direct a particular subject to a particular treatment thus preventing treatment allocation bias. Ulcer measurements will be carried out using the ImageIQ EDCIQ mobile imaging system which will minimize subjectivity in theses assessments.

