10.2 HANDLING OF MISSING AND INCOMPLETE DATA

The methods used to handle missing or incomplete data for the efficacy and safety measures will be detailed in the Statistical Analysis Plan. For purposes of the primary endpoint, in cases where a photograph is not taken, the Last Observation Carried Forward (LOCF) method will be used. Sensitivity analyses will be conducted as detailed in the following sections to examine the impact of these derivations on the conclusions relating to the primary endpoint.

For purposes of assessments of wound area (and subsequent reductions over the study period), in cases where Study Visit 7 is not attended by the subject, or the area value at the assessment is not recorded or known, the Last Observation Carried Forward (LOCF) method (excluding Study Visit I) will be used.

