10.3 EFFICACY

10.3.1 Primary Efficacy

The primary endpoint of the study is the proportion of subjects achieving complete debridement over the 6-week treatment period and will be analyzed as follows using the Full Analysis Set. For purposes of the primary analysis, the status of complete debridement will be assessed from photographs by two independent reviewers. In the event of disagreement between the two reviewers, the complete debridement status agreed during the consensus meetings will be analyzed in the primary analysis. In cases where a photograph is not taken, the Last Observation

Carried Forward (LOCF) method will be used. Sensitivity analyses will be conducted as detailed in the following sections.

An initial logistic regression model will contain covariates for treatment, baseline (defined as Study Visit 1) ulcer area, baseline percentage of nonviable tissue, and duration of ulcer. A forward selection procedure will be used for the addition of other baseline covariates with an F-value to attain a significance level of 0.1. Further baseline covariates to be assessed as part of this procedure include: subject age, baseline (maximum) ulcer depth, baseline PUSH and WBS scores.

The resulting analysis presented will correspond to the final model from the forward selection procedure. The results for the initial model will also be presented. For each of the effects in the initial and final model, the p-value, odds-ratio and corresponding 95% confidence interval will be presented. Secondary subgroup analyses may be conducted as a result of the covariate analyses. Additionally, treatment will be fitted on its own in a further logistic regression model. In each case, the residuals will be examined for outliers using influence plots of diagnostic statistics; further details are included in the SAP.

Cross-tabulations of each of the covariates (continuous covariates will be categorized for purposes of the cross-tabulations) with treatment and achievement of complete debridement, will be generated for each of the baseline covariates included in the final model.

The 95% confidence interval (unadjusted for all covariates) for the difference between treatments in proportion achieving complete debridement within 6 weeks will be generated along with the Chi-square or Fisher's Exact test p-value using the Per Protocol population depending on minimum expected cell.

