Two separate sensitivity analyses will be performed to ensure that the efficacy findings are not reliant on assumptions made in the analysis, derivations, or changes agreed between the blinded review panel. The analysis for the proportion of subjects achieving completed debridement will be repeated with the following modifications using the Full Analysis Set only:

- 1) In cases where there is initial disagreement (pre-consensus meeting) between the two blinded reviewers, the "worst case" value will be used. That is, in cases where one reviewer found the ulcer to have achieved complete debridement whilst the remaining reviewer found there to still be (>0%) necrotic, non-viable tissue present, the following will be imputed:

 Complete debridement achieved = No.
- 2) In cases where there is initial disagreement (pre-consensus meeting) between the two blinded reviewers, the "best case" value will be used. That is, in cases where one reviewer found the ulcer to have achieved complete debridement whilst the remaining reviewer found there to still be (>0%) necrotic, non-viable tissue present, the following will be imputed:

Complete debridement achieved = Yes.

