11. SAMPLE SIZE JUSTIFICATION

A previous study (7) with a design essentially identical to the present study demonstrated highly significant differences between treatment groups for achievement of complete debridement (85% vs. 29%, P<0.003), reduction in % area of non-viable tissue for each week (P<0.002), and in reduction in wound area (P<0.009). The sample size of this previous trial was 27 subjects, 13 in the SANTYL group, and 14 in the hydrogel group. Based on the reported outcomes in the previous trial, 26 subjects are required to detect a difference in the primary endpoint: the proportion of ulcers achieving complete debridement during the 6-week treatment period. This relates to a Fisher's Exact test assuming 85% vs 29% in the proportion of ulcers achieving complete debridement. To allow for 15% drop-out rate throughout the 6-week treatment period, a total of 32 subjects will be randomized (16 per treatment) in an equal allocation ratio for SANTYL and hydrogel. In the previous studies quoted, the secondary endpoints including reduction in % area of non-viable tissue and reduction in wound area were found to reach significance with similar numbers.

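### The primary efficacy set is called intent-to-treat but omits randomized subjects with no post-baseline visit, and no planned efficacy analysis brings them back

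*Combined protocol and SAP*

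**What the plan says.** Section 10.1 sets three conditions for the intent-to-treat population, which it also calls the Full Analysis Set: randomization, a valid baseline ulcer measurement, and that the subject "complete at least one post-baseline visit". It makes this set the primary one for efficacy. The per-protocol set is drawn from within it. Section 10.3.1 states that the primary endpoint "will be analyzed as follows using the Full Analysis Set". It specifies a covariate-adjusted logistic regression, an extended model after forward selection, and a model with treatment alone. The chi-square or Fisher test is assigned to the per-protocol population.

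For missing photographs, section 10.2 says that "in cases where a photograph is not taken, the Last Observation Carried Forward (LOCF) method will be used". The two sensitivity analyses of the primary endpoint concern disagreement between the photograph reviewers and are to be "repeated with the following modifications using the Full Analysis Set only".

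On masking, section 8.2 accepts that "double-blinding of the study medication is not possible"; only the photograph assessors are blinded. Section 9.2 requires the Exit Visit of every subject who discontinues. Section 11 enlarges the sample "To allow for 15% drop-out rate throughout the 6-week treatment period".

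**The concern.** An intent-to-treat set keeps every randomized subject in the assigned arm, so that the comparison rests on the randomization. Here membership depends on an event after the first application of a product that staff and subject can identify. Blinded reading of photographs protects the assessment of the outcome. It does not influence who leaves.

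A subject lost before any post-baseline visit drops out of the denominator and is not counted as a failure to debride. This raises the observed success rate in whichever arm loses the subject. In a confirmatory trial with 16 subjects per arm, one subject is 6.25% of an arm (1/16), enough to move a borderline result.

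The exclusion is also avoidable. Every ulcer must be at least 85% necrotic at entry (sections 7.1 and 7.2), and at least one independent reviewer must read the Visit 1 image before randomization (section 9.1.2). Each randomized subject therefore has a known starting status of not debrided.

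**Working it through.** **1. The plan's own sample size.** Inputs from section 11: 85% vs 29%, Fisher's exact test, 15% drop-out; from section 10: two-sided 5%. Power is not stated, so I assume 80%. Exact power, by enumerating both binomials, is 74.2% with 12 per arm and 80.9% with 13 per arm, hence 26 evaluable. For drop-out, 13/(1 − 0.15) = 15.3, rounded up to 16 per arm, or 32. The stated figures reproduce.

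**2. How many subjects are exposed.** Expected drop-out is 0.15 × 32 = 4.8 subjects over six weeks. If it were spread evenly (an assumption), the first week would hold 4.8/6 = 0.8 subjects across both arms. Any of these who attend the Exit Visit stay in the set.

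**3. Whether any analysis restores them.**
- Primary models: Full Analysis Set, so no.
- Chi-square or Fisher comparison: per-protocol set, a subset of the same population, so no.
- Two reviewer-disagreement analyses: Full Analysis Set only, so no.
- Time to debridement: Full Analysis Set, repeated per protocol, so no.
- Safety population: used for adverse events, not efficacy.

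**4. Effect on the primary comparison.** All counts are assumed. With treatment alone in the logistic model, the Wald statistic for a successes and b failures on SANTYL, and c successes and d failures on hydrogel, is z = ln(ad/bc) / √(1/a + 1/b + 1/c + 1/d).

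One SANTYL leaver, with 12 SANTYL and 7 of 16 hydrogel subjects debrided:
- Plan's set, 12/15 (80.0%) vs 7/16 (43.8%): ln(12×9/(3×7)) = ln 5.143 = 1.638; SE = √(1/12 + 1/3 + 1/7 + 1/9) = 0.819; z = 2.00; p = 0.046.
- All randomized, 12/16 (75.0%) vs 7/16: ln(12×9/(4×7)) = ln 3.857 = 1.350; SE = √(1/12 + 1/4 + 1/7 + 1/9) = 0.766; z = 1.76; p = 0.078.

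Other tables by the same formula:

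| Early leavers | Plan's set | p | All randomized | p |
|---|---|---|---|---|
| 1 SANTYL | 11/15 vs 5/16 | 0.024 | 11/16 vs 5/16 | 0.039 |
| 2 SANTYL | 11/14 vs 5/16 | 0.014 | 11/16 vs 5/16 | 0.039 |
| 1 SANTYL | 13/15 vs 5/16 | 0.004 | 13/16 vs 5/16 | 0.007 |
| 2 SANTYL | 10/14 vs 5/16 | 0.033 | 10/16 vs 5/16 | 0.082 |
| 1 hydrogel | 11/16 vs 5/15 | 0.054 | 11/16 vs 5/16 | 0.039 |

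The first three rows keep their conclusion. The fourth changes but needs two losses, both on SANTYL. The last shows the effect in the other direction: losing a hydrogel subject raises the hydrogel rate and weakens the comparison.

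**5. Power if leavers count as failures.** Fisher, 16 per arm, equal early loss in both arms, and 85% and 29% taken as rates among subjects who stay:
- none: 86.0%
- 5% (0.95 × 85% = 80.8% vs 0.95 × 29% = 27.6%): 80.5%
- 10% (76.5% vs 26.1%): 74.6%
- 15%, all leaving early (72.3% vs 24.7%): 68.3%

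For a like-for-like view, one leaver per arm (6.25%) gives about 79.1% when counted as a failure. The current set would have 15 per arm and 81.3%.

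**The case against.** The strongest reply is that the gap is narrow. Section 9.2 covers voluntary withdrawal and withdrawal for safety and demands the Exit Visit in all cases. Subjects are in-patients, so that visit is practical. A reader might infer that subjects who stop early for intolerance or deterioration vanish from the analysis. The documents do not support that: a subject who attends the Exit Visit stays in the set and counts as not debrided if necrotic tissue remains. This part of the reply stands. It leaves subjects who have no post-baseline visit, whose attendance section 9.2 cannot guarantee.

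A reader might also treat the whole 15% drop-out, about 5 of 32, as the number excluded. That figure covers six weeks, and step 2 shows why it overstates the exposure.

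Third, a reader might apply Fisher's test to 11/15 vs 5/16 (p=0.032) and 11/16 vs 5/16 (p=0.076) and conclude that the plan's result reverses there. The plan does not use Fisher on this set. Under its treatment-only logistic model both tables are below 0.05.

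Finally, section 10.2 is silent on whether Visit 1 may be carried forward for the primary endpoint; it excludes Visit 1 expressly only for wound area. Carrying Visit 1 forward is therefore a possible reading, not a stated rule. Section 10 defers detail to a separate SAP. None is in the text supplied, so any change made there cannot be checked.

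**Conclusion.** The point holds in limited form. The set labelled intent-to-treat carries an avoidable post-randomization exclusion, and no planned efficacy analysis shows what difference it makes. The number affected is unknown and probably small, perhaps none or one. The split by arm is also unknown, so the documents do not support a claim that the rule favours SANTYL.

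At this sample size one excluded subject can move a borderline result across 0.05 (0.046 against 0.078). Near the planning rates the conclusion does not change (13/15 or 13/16 vs 5/16). These p-values rest on assumed counts and on the treatment-only model; the covariate-adjusted result cannot be computed without data. The change is worth making because it is cheap and restores the comparison that the label promises.

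**What to change.** In section 10.1 and the SAP, define the primary efficacy population as all randomized subjects, analysed in the arm assigned. For the primary endpoint, state that a subject with no post-baseline photograph counts as not completely debrided; this also settles the silence on Visit 1 in section 10.2. Keep the present set as a supportive analysis, and report by arm, with reasons, every randomized subject whom it leaves out.

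For time to debridement, the section 10.3.2 rule would censor such a subject at day 0, which adds nothing to the main Cox estimate. The change matters only in the existing sensitivity analysis that censors at day 42.

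The cost is a sentence or two of text and no new data. Success rates fall slightly in an arm with early leavers, and power falls as in step 5: from 86.0% with none to about 80.5% if 5% per arm leave early. If 85% and 29% already count drop-outs as failures, power stays at 86.0%.

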10.2 HANDLING OF MISSING AND INCOMPLETE DATA

The methods used to handle missing or incomplete data for the efficacy and safety measures will be detailed in the Statistical Analysis Plan. For purposes of the primary endpoint, in cases where a photograph is not taken, the Last Observation Carried Forward (LOCF) method will be used. Sensitivity analyses will be conducted as detailed in the following sections to examine the impact of these derivations on the conclusions relating to the primary endpoint.

For purposes of assessments of wound area (and subsequent reductions over the study period), in cases where Study Visit 7 is not attended by the subject, or the area value at the assessment is not recorded or known, the Last Observation Carried Forward (LOCF) method (excluding Study Visit I) will be used.

10.3 EFFICACY

10.3.1 Primary Efficacy

The primary endpoint of the study is the proportion of subjects achieving complete debridement over the 6-week treatment period and will be analyzed as follows using the Full Analysis Set. For purposes of the primary analysis, the status of complete debridement will be assessed from photographs by two independent reviewers. In the event of disagreement between the two reviewers, the complete debridement status agreed during the consensus meetings will be analyzed in the primary analysis. In cases where a photograph is not taken, the Last Observation

Carried Forward (LOCF) method will be used. Sensitivity analyses will be conducted as detailed in the following sections.

An initial logistic regression model will contain covariates for treatment, baseline (defined as Study Visit 1) ulcer area, baseline percentage of nonviable tissue, and duration of ulcer. A forward selection procedure will be used for the addition of other baseline covariates with an F-value to attain a significance level of 0.1. Further baseline covariates to be assessed as part of this procedure include: subject age, baseline (maximum) ulcer depth, baseline PUSH and WBS scores.

The resulting analysis presented will correspond to the final model from the forward selection procedure. The results for the initial model will also be presented. For each of the effects in the initial and final model, the p-value, odds-ratio and corresponding 95% confidence interval will be presented. Secondary subgroup analyses may be conducted as a result of the covariate analyses. Additionally, treatment will be fitted on its own in a further logistic regression model. In each case, the residuals will be examined for outliers using influence plots of diagnostic statistics; further details are included in the SAP.

Cross-tabulations of each of the covariates (continuous covariates will be categorized for purposes of the cross-tabulations) with treatment and achievement of complete debridement, will be generated for each of the baseline covariates included in the final model.

The 95% confidence interval (unadjusted for all covariates) for the difference between treatments in proportion achieving complete debridement within 6 weeks will be generated along with the Chi-square or Fisher's Exact test p-value using the Per Protocol population depending on minimum expected cell.

Two separate sensitivity analyses will be performed to ensure that the efficacy findings are not reliant on assumptions made in the analysis, derivations, or changes agreed between the blinded review panel. The analysis for the proportion of subjects achieving completed debridement will be repeated with the following modifications using the Full Analysis Set only:

- 1) In cases where there is initial disagreement (pre-consensus meeting) between the two blinded reviewers, the "worst case" value will be used. That is, in cases where one reviewer found the ulcer to have achieved complete debridement whilst the remaining reviewer found there to still be (>0%) necrotic, non-viable tissue present, the following will be imputed:

 Complete debridement achieved = No.
- 2) In cases where there is initial disagreement (pre-consensus meeting) between the two blinded reviewers, the "best case" value will be used. That is, in cases where one reviewer found the ulcer to have achieved complete debridement whilst the remaining reviewer found there to still be (>0%) necrotic, non-viable tissue present, the following will be imputed:

Complete debridement achieved = Yes.

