10. STATISTICAL DESIGN

A formal Statistical Analysis Plan (SAP) (also referenced to as the Statistical Considerations) will be written and finalized prior to database lock. The SAP will detail the summaries and analyses to be performed.

Smith & Nephew Wound Management Global Medical and Clinical Affairs Department will conduct data management and statistical analysis. Unless otherwise stated, all significance tests and hypothesis testing will be two-sided, performed at the 5% significance level. Resulting p-values will be quoted and 95% two-sided confidence intervals will be generated where appropriate. All analyses will be performed in SAS v9.4 (or later).

Where data summaries are specified, categorical and ordinal variables will be summarized using frequency distributions which will detail the number and percentage of subjects which fall into each category. Continuous variables will be summarized using the following summary statistics: mean, median, standard deviation, minimum and maximum values, and number of observations.

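### The trial is sized on Fisher's exact test, but its primary result comes from a forward-selected logistic model with no named treatment test and no rule for separation

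*Combined protocol and SAP*

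**What the plan says.** Protocol Section 11 gives 26 subjects as the requirement for a Fisher's exact test at 85% vs 29%, raised to 32 (16 per arm) for 15% drop-out. It states no power.

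Section 10.3.1 describes a different analysis. The primary endpoint "will be analyzed as follows using the Full Analysis Set". The starting logistic model holds treatment, baseline ulcer area, baseline percentage of non-viable tissue and ulcer duration. Then a "forward selection procedure will be used for the addition of other baseline covariates with an F-value to attain a significance level of 0.1"; the candidates are age, maximum depth, PUSH and WBS. Of the outcome it says: "The resulting analysis presented will correspond to the final model from the forward selection procedure".

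On reporting: "For each of the effects in the initial and final model, the p-value, odds-ratio and corresponding 95% confidence interval will be presented". The initial model is also shown, and "Additionally, treatment will be fitted on its own in a further logistic regression model". The simple two-group comparison appears only as a "Chi-square or Fisher's Exact test p-value using the Per Protocol population depending on minimum expected cell".

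Section 10.1 says "The ITT population is the primary efficacy population" and makes Per Protocol secondary. Section 10 sets the error rate: "all significance tests and hypothesis testing will be two-sided, performed at the 5% significance level".

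**The concern.** The test that justifies the sample size is not assigned to the primary population. The analysis that is assigned there has no stated power, and three things about it are open or depend on the data.

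- **Terms in the model.** Covariates enter according to their association with the outcome in the same 32 subjects. The F-value named as the entry criterion is not a standard statistic for logistic regression.
- **Test of treatment.** Wald, likelihood-ratio, score and exact tests can differ materially at this size, and none is named.
- **Separation.** If treatment, alone or combined with covariates, predicts the outcome perfectly, the maximum-likelihood odds ratio is infinite and the Wald test is useless. No rule covers this.

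Three logistic models are reported. If the final one separates, moving to another model or test would be a choice made after seeing the data. That is serious in a small trial meant to confirm an earlier result.

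**Working it through.** **Inputs from the protocol.** Two-sided 5% level (Section 10); 85% vs 29%, 13 per arm required and 16 per arm randomised (Section 11); four forced terms, four candidates, entry at 0.1 (Section 10.3.1).

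**Assumptions, because the documents give no values.** Covariate distributions and prognostic strength; a score test for entry in place of the F-value; selection stops if the model separates; allocation balanced within size stratum. Two covariate sets were used: (i) independent normals; (ii) skewed area and duration, uniform percentage of non-viable tissue, PUSH correlated 0.7 with log area, WBS correlated -0.5 with depth. Ranges below span both sets.

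**Step 1: reproduce Section 11.** Exact power = Σₐ Σ_b Bin(a; n, 0.85) · Bin(b; n, 0.29) · 1[two-sided Fisher p ≤ 0.05].

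- n = 12: 74.2%
- n = 13: 80.9%
- n = 16: 86.0%

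So 26 fits an unstated 80% target. For drop-out, 13 / 0.85 = 15.3, rounded up to 16 per arm, or 32. Section 11 is sound for the test it names.

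**Step 2: separation with treatment alone.** There is no finite odds ratio if all 16 SANTYL ulcers respond or none of the 16 hydrogel ulcers do (other routes are negligible):

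- 0.85¹⁶ = 0.0743
- 0.71¹⁶ = 0.0042
- 1 − (1 − 0.0743)(1 − 0.0042) = 0.078

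**Step 3: the full Section 10.3.1 procedure.** The treatment-only and Fisher rows are exact. The other rows come from 6,000 simulated trials per scenario (95% simulation error about ±1.1 points for power and ±0.8 for type I error). Separation was confirmed by linear programming, and separated fits count as Wald non-significant. Covariates are not prognostic. Type I error is at a common rate of 50% or 57%.

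| Analysis, N = 32 | No finite odds ratio at 85% vs 29% | Wald power | Wald type I error | Likelihood-ratio type I error |
|---|---|---|---|---|
| Treatment only | 7.8% | 85.0% | 4.8-5.0% | 5.2% |
| Four forced terms | 8.0-8.2% | 82-83% | 5.0-5.6% | 7.0-7.6% |
| Final selected model | 14.2-14.3% | 73-74% | 6.3-6.8% | 10.3-10.7% |

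Fisher: power 86.0%, type I error about 2%. Likelihood-ratio power is 93.3% with treatment only and 93-94% for the final model. At least one covariate was added in 40-45% of trials.

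**Step 4: where each fault comes from.** Among finite final-model fits, Wald power is 85-86.5%. With 14.2% separated, 0.858 × 0.85 = 0.729 and 0.858 × 0.865 = 0.742, so the power loss is the separated trials. Type I error has another cause. With no effect, the final model separates in only 0.3-0.5% of trials, which adds under 0.5 points to the likelihood-ratio error. The rise from 5.2% to 7.0-7.6% is small-sample bias from the forced terms; the further rise to 10.3-10.7% comes from selection.

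**Step 5: sensitivity.**

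- Area, duration and depth each with log-odds 0.5 per SD: final model separated in 21-23%, Wald power 65-67%.
- Common rate 29%: likelihood-ratio type I error 11.9-12.2%, Wald 4.8%.
- Common rate 57% with prognostic covariates: likelihood-ratio 12.4%, Wald 5.2-5.8%.
- 30 subjects analysed (4,000 trials): separated 18%, Wald power 67%, Fisher about 82%, likelihood-ratio type I error 10.3-11.3%.
- A second simulation (8,000 trials, independent normals, not prognostic) with a looser definition that includes near-separation: 18% flagged; Wald power 73.8%, or 71.5% with all flagged fits counted as failures; likelihood-ratio type I error 10.3% at a common 57%.

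**The case against.** The strongest reply has four parts.

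- **The two harms cannot both occur.** Low power belongs to Wald and inflated error to the likelihood ratio. This is correct. It also means that neither test gives the final model both Fisher's power and a 5% error rate.
- **The power loss is a scoring convention.** At 85% vs 29%, Fisher is significant in about 99% of the separated trials, and 7.8 of the 14.2 points of separation arise with treatment alone. This stands: these are mostly strong results that the planned output cannot express, and selection adds only about 6 points. It is still a reason to set the rule in advance.
- **The SAP may settle it.** Section 10 promises an SAP before database lock, and its text is not in the file reviewed. It could name the test and a separation rule. It could not stop the selected model being the result without departing from Section 10.3.1.
- **Sizing on a simple test and analysing with an adjusted model is common, and the initial and treatment-only models are also reported.** Both are true. The mismatch would matter little if the adjusted model were fixed and one test were named, but none of the reported models other than the selected one is designated as the result.

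**Conclusion.** The concern holds, and it should be resolved before the data are analysed. The textual part needs no assumption: the sizing test is assigned only to the secondary population, the primary result comes from a data-selected model, and the protocol states neither a deciding test nor a separation rule.

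The size depends on assumed covariates and a substituted entry test. With non-prognostic covariates at N = 32, the final model has either about 73% Wald power (Fisher 86%) or about 10% likelihood-ratio type I error (stated 5%). In the prognostic scenarios examined, Wald power was lower and likelihood-ratio error higher. Confidence is high in the direction of both effects and lower in the exact percentages.

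**What to change.** In Section 10.3.1, name one prespecified primary test of treatment in the Full Analysis Set:

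- **Option (a):** Fisher's exact test. It matches Section 11 and leaves N unchanged (power 80.9% at 13 per arm, 86.0% at 16).
- **Option (b):** a fixed logistic model with treatment and the randomisation size stratum (or baseline area), fitted by Firth-penalised or exact methods, with a matching profile-likelihood or exact confidence interval. For Firth with the stratum, simulated power is 93% and type I error 4.6-5.3%. Both remain defined under separation.

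Make the four-covariate and forward-selected models supportive, replace the F-value with a named entry test, and state which test of treatment they use and how separation will be reported. In Section 11, state the power of the chosen test.

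The cost is protocol and SAP wording, with no new subjects or data. The multi-covariate model is no longer the headline, and option (a) is conservative (type I error about 2%) and ignores the stratum.
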